1.3. Sample Size and Power

The primary goal of this study is to evaluate the efficacy of the combination of tirabrutinib and idelalisib with obinutuzumab in relapsed and refractory CLL. The evaluation will be based on the estimation of the CR rate (including CR and CR with incomplete recovery of the bone marrow (CRi)) and its corresponding exact confidence interval. Approximately 30 subjects will be enrolled into Arm B, which will result in the 90% confidence interval (CI) of the observed CR rate to be within $\pm 17.0\%$. The 90% CI for a given observed CR rate is provided in [Table 1-1](#).

Table 1-1. 90% Confidence Intervals at Different CR Rates

Sample Size	Observed CR Rate	90% Confidence Interval using Clopper-Pearson Method
30	20%	(9.1%, 35.7%)
30	30%	(16.6%, 46.5%)
30	40%	(25.0%, 56.6%)
30	50%	(33.9%, 66.1%)
30	60%	(43.4%, 75.1%)

With Amendment 3, randomization was discontinued. All subsequent subjects will be enrolled to Arm B. A total of approximately 6 subjects in Arm A and 30 subjects in Arm B will be enrolled, thus the total sample size for the study will be approximately 36 subjects.

2. TYPE OF PLANNED ANALYSIS

2.1. Interim Analysis

No formal interim analysis is planned.

This study does not have a data monitoring committee (DMC). Therefore, no analyses will be conducted for the DMC.

2.2. Final Analysis

After all subjects have discontinued/completed the study, outstanding data queries have been resolved or adjudicated as unresolvable, and the data have been cleaned and finalized, the final analysis of the data will be performed.

2.3. Follow-up Analysis

No follow-up analysis is planned.

3. GENERAL CONSIDERATIONS FOR DATA ANALYSES

Analysis results will be presented using descriptive statistics. For categorical variables, the number and percentage of subjects in each category will be presented; for continuous variables, the number of subjects (n), mean, standard deviation (StD) or standard error (SE), median, first quartile (Q1), third quartile (Q3), minimum, and maximum will be presented.

By-subject listings will be presented for all subjects in the All Enrolled Analysis Set and sorted by subject ID number, visit date, and time (if applicable). Data collected on log forms, such as AEs, will be presented in chronological order within the subject. The treatment group to which subjects were randomized/initially assigned will be used in the listings. Age, sex at birth, race, and ethnicity for each subject will be presented in the listings, as space permits.

3.1. Analysis Sets

Analysis sets define the subjects to be included in an analysis. Analysis sets and their definitions are provided in this section. The analysis set will be identified and included as a subtitle of each table, figure, and listing.

For each analysis set, the number and percentage of subjects eligible for inclusion will be summarized by treatment group.

A listing of reasons for exclusion from analysis sets will be provided by subject.

This study was initially designed as a randomized study. With Amendment 3, randomization was discontinued, and all subsequent subjects will be enrolled into Arm B. There is no intention to compare the treatments, so intent-to-treat Analysis Set will not be used; instead, All Enrolled Analysis Set defined in Section 3.1.1 and Full Analysis Set defined in Section 3.1.2 will be used.

3.1.1. All Enrolled Analysis Set

All Enrolled Analysis Set includes all subjects who received a study subject identification number in the study after screening.

3.1.2. Full Analysis Set

The Full Analysis Set (FAS) includes all subjects who received at least 1 dose of any study drug with treatment group designated according to the planned treatment. This is the primary analysis set for efficacy analyses.

3.1.3. Safety Analysis Set

The Safety Analysis Set includes all subjects who took at least 1 dose of study drug. This is the primary analysis set for safety analyses.

CCI

3.2. Subject Grouping

For analyses based on FAS, subjects will be grouped according to the treatment they are assigned to at randomization or enrollment. For analyses based on the Safety Analysis Set, subjects will be grouped according to the actual treatment received. The actual treatment received will differ from the treatment assigned at randomization or enrollment only when their actual treatment differs from assigned treatment for the entire treatment duration.

CCI

3.3. Strata and Covariates

Subjects will be randomly assigned to treatment groups via the interactive web response system (IWRS) in a 1:1 ratio using a stratified randomization schedule. Stratification will be based on the presence of del17p/TP53mut in CLL cells. If there are discrepancies in stratification factor values between the IWRS and the clinical database, the values recorded in the clinical database will be used for analyses.

With Amendment 3, randomization was discontinued. All subsequent subjects were enrolled into Arm B. There is no intention to compare the treatments. No covariates will be included in efficacy analyses.

3.4. Examination of Subject Subgroups

Primary and secondary efficacy endpoints will be examined in the subgroups based on randomization stratification factor (either del17p or TP53mut versus neither del17p nor TP53mut) for each arm. CCI

3.5. Multiple Comparisons

Not applicable.

3.6. Missing Data and Outliers

3.6.1. Missing Data

In general, missing data will not be imputed unless methods for handling missing data are specified. Exceptions are presented in this document.

For missing last dosing date of study drug, imputation rules are described in Section 4.2.1. The handling of missing or incomplete dates for CLL diagnosis is described in Section 5.3; for prior anti-cancer therapy in Section 5.4, for new anti-cancer therapy in Section 6.3.2, for death in Section 6.3.1, for AE onset in Section 7.1.5.2, and for prior and concomitant medications in Section 7.4.

3.6.2. Outliers

Outliers will be identified during the data management and data analysis process, but no sensitivity analyses will be conducted. All data will be included in the data analysis.

3.7. Data Handling Conventions and Transformations

The following conventions will be used for the imputation of date of birth when it is partially missing or not collected:

- If only month and year of birth is collected, then “15” will be imputed as the day of birth
- If only year of birth is collected, then “01 July” will be imputed as the day and month of birth
- If year of birth is missing, then date of birth will not be imputed. In general, age collected at Day 1 (the first dosing date of study drug) (in years) will be used for analyses and presented in listings. If age at Day 1 is not available for a subject, then age derived based on date of birth and the Day 1 visit date will be used instead. If an enrolled subject was not dosed with any study drug, the randomization or enrollment date will be used instead of the Day 1 visit date. For screen failures, the date the first informed consent was signed will be used for the age derivation. Age required for longitudinal and temporal calculations and analyses (eg, estimates of creatinine clearance, age at date of AE) will be based on age derived from date of birth and the date of the measurement or event, unless otherwise specified.

Non-PK data that are continuous in nature but are less than the lower limit of quantitation (LOQ) or above the upper LOQ will be imputed as follows:

- A value that is 1 unit less than the LOQ will be used to calculate descriptive statistics if the datum is reported in the form of “< x” (where x is considered the LOQ). For example, if the values are reported as < 50 and < 5.0, values of 49 and 4.9, respectively, will be used to calculate summary statistics. An exception to this rule is any value reported as < 1 or < 0.1, etc. For values reported as < 1 or < 0.1, a value of 0.9 or 0.09, respectively, will be used to calculate summary statistics.
- A value that is 1 unit above the LOQ will be used to calculate descriptive statistics if the datum is reported in the form of “> x” (where x is considered the LOQ). Values with decimal points will follow the same logic as above.
- The LOQ will be used to calculate descriptive statistics if the datum is reported in the form of “≤ x” or “≥ x” (where x is considered the LOQ).

If methods based on the assumption that the data are normally distributed are not adequate, analyses may be performed on transformed data or nonparametric analysis methods may be used, as appropriate.

CCI [REDACTED]

[REDACTED]

[REDACTED]

[REDACTED]

[REDACTED]

[REDACTED]

3.8. Analysis Visit Windows

3.8.1. Definition of Study Day

Study day will be calculated from the first dosing date of study drug and derived as follows:

- For postdose study days: Assessment Date – First Dosing Date + 1
- For days prior to the first dose: Assessment Date – First Dosing

Therefore, study day 1 is the day of first dose of study drug administration.

3.8.2. Analysis Visit Windows

The nominal visit as recorded on the CRF will be used when data are summarized by visit. Any data relating to unscheduled visits will not be assigned to a particular visit or time point.

However, the following exceptions will be made:

- An unscheduled visit prior to the first dosing of study drug may be included in the calculation of the baseline value, if applicable.
- Unscheduled visits after the first dosing of study drug will be included in determining the maximum postbaseline toxicity grade.

3.8.2.1. Analysis Visit Windows for Primary/Secondary Efficacy Endpoints

The analysis windows for Week 25 response assessment and Week 25 MRD assessment are defined as $24 \times 7 \pm 28$ days (inclusive) starting from first dose.

3.8.3. Selection of Data in the Event of Multiple Records in an Analysis Visit Window

Depending on the statistical analysis method, single values may be required for each analysis window. For example, change from baseline by visit usually requires a single value, whereas a time-to-event analysis would not require 1 value per analysis window.

If multiple valid, nonmissing measurements exist in an analysis window, records will be chosen based on the following rules if a single value is needed:

- For baseline, the last nonmissing value on or prior to the first dosing date of study drug will be selected, unless specified differently. If there are multiple records with the same time or no time recorded on the same day, the baseline value will be the average of the measurements for continuous data, or the measurement with the lowest severity (eg, normal will be selected over abnormal for safety electrocardiogram [ECG] findings) for categorical data.
- For postbaseline values:
 - The record closest to the nominal day for that visit will be selected.
 - If there are 2 records that are equidistant from the nominal day, the later record will be selected.
 - If there is more than 1 record on the selected day, the average will be taken for continuous data and the worse severity will be taken for categorical data, unless otherwise specified.

4. SUBJECT DISPOSITION

4.1. Subject Enrollment and Disposition

A summary of subject enrollment will be provided by treatment group for each investigator and overall. The summary will present the number and percentage of subjects enrolled. For each column, the denominator for the percentage calculation will be the total number of subjects analyzed for that column.

A listing of subjects with discrepancies in the value used for stratification assignment between the IWRS and the clinical database at the time of data finalization will be provided.

A summary of subject disposition will be provided by treatment group. This summary will present the number of subjects screened, the number of subjects randomized or enrolled, the number of subjects who were randomized or enrolled but not dosed, and the number of subjects in each of the categories listed below by treatment group:

- Safety Analysis Set
- Tirabrutinib completion status
 - Completed study drug dosing as specified per protocol
 - Discontinued study drug dosing with reasons
- Idelalisib completion status
 - Completed study drug dosing as specified per protocol
 - Discontinued study drug dosing with reasons
- Obinutuzumab completion status
 - Completed study drug dosing as specified per protocol
 - Discontinued study drug dosing with reasons
- Study completion status
 - Completed the protocol-planned duration of the study
 - Discontinued the study with reasons

For the status of study drug and study completion and reasons for discontinuation, the number and percentage of subjects in each category will be provided. The denominator for the percentage calculation will be the total number of subjects in the All Enrolled Analysis Set corresponding to that column. In addition, a flowchart will be provided to depict the disposition.

The following by-subject listings will be provided by subject identification (ID) number in ascending order to support the above summary tables:

- Reasons for study drug or study discontinuation
- Reasons for screen failure (will be provided by screening ID number in ascending order)

4.2. Extent of Study Drug Exposure and Adherence

Extent of exposure to study drug will be examined by assessing the total duration of exposure to study drug and the level of adherence to the study drug specified in the protocol.

4.2.1. Duration of Exposure to Study Drug

Total duration of exposure to study drug will be defined as last dosing date minus first dosing date plus 1, regardless of any temporary interruptions in study drug administration, and will be expressed in weeks using up to 1 decimal place (eg, 4.5 weeks). If the last study drug dosing date is missing, the latest date among the study drug end date, clinical visit date, laboratory sample collection date, and vital signs assessment date will be used.

The total duration of exposure to study drug will be summarized using descriptive statistics. For tirabrutinib and idelalisib, the number (ie, cumulative counts) and percentage of subjects exposed will be summarized by the following time periods: ≥ 1 day, ≥ 1 week, ≥ 2 weeks, ≥ 3 weeks, ≥ 4 weeks, ≥ 6 weeks, ≥ 8 weeks, every 4 weeks starting from 8 weeks to 32 weeks, and then every 12 weeks starting from 32 weeks until 104 weeks (if appropriate). For obinutuzumab, the number of infusions will be summarized using descriptive statistics. Summaries will be provided by treatment group for the Safety Analysis Set.

The number and percentage of subjects who have dose reduction or interruptions, and the reasons, will be summarized by treatment.

No formal statistical testing is planned.

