3.5. Duration of Study

This study will continue to monitor subjects for up to 30 days post end of treatment, or up to Week 25 should a subject discontinue treatment prior to Week 25 for reasons other than disease progression.

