6.7. End of Treatment

The EOT visit should be scheduled for 30 days following discontinuation of all study treatment to satisfy the requirement for a 30-day post-treatment safety assessment. Please consider enrollment of subjects at EOT in the non-interventional GCLLSG CLL registry for subjects that did not enroll at screening.

For subjects that permanently discontinue all study treatment prior to the Week 25 visit without experiencing disease progression, the Week 25 Day 1 visit should be performed on schedule per the Study Procedures Table ([Appendix 2](#)).

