7.1.5. Treatment-Emergent Adverse Events

7.1.5.1. Definition of Treatment-Emergent Adverse Events

Treatment-emergent adverse events (TEAEs) are defined as 1 or both of the following:

- Any AEs with an onset date on or after the study drug start date and no later than 30 days after permanent discontinuation of study drug
- Any AEs leading to discontinuation of study drug

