- 14 CLL immunophenotyping, karyotyping and FISH, TP53 and IgHV mutation status, CD38 and ZAP70 expression will be evaluated from peripheral blood at screening. In the event of disease progression, only FISH and TP53 will be evaluated.
- 15 Tumor evaluation by CT scan (preferred) or MRI of neck, chest, abdomen, and pelvis will be performed at screening (unless scan was already completed up to 42 days prior to first dose). At the Week 25 visit, the same type of evaluation should be performed on those body regions which showed involvement by CLL at screening. An additional CT may be obtained on protocol per investigator discretion following evidence of an improvement in clinical response if the response assessment at the Week 25 visit is less than a complete response or in the event of suspected disease progression.
- 16 A bone marrow evaluation is required in the screening window for subjects without radiographic evidence of disease. Bone marrow aspirate and biopsy should be performed at Week 25 for subjects fulfilling clinical response criteria for CR or CRi per the modified IWCLL 2008 criteria. MRD should be assessed from bone marrow aspirate at the reference laboratory in Kiel; CCI
- CCI
- 17 Qualitative treatment response assessment based on physical exam, laboratory parameters and presence of B-symptoms should be performed every 4 weeks until Week 33 Day 1 and then at all scheduled visits thereafter following the modified IWCLL 2008 criteria, with the exception of lymphadenopathy, hepatomegaly, splenomegaly, and bone marrow. Assessment of response per modified IWCLL 2008 criteria should also be recorded at the completion of 24 weeks on treatment and subsequent to any CT and/or bone marrow biopsy that is repeated while on study.
- 18 Following evaluation of the safety data for the first 6 subjects enrolled in each treatment arm, the Safety Review Team (SRT) will determine if weekly clinical evaluation should continue for the duration of the study.
- 19 The EOT visit should be scheduled for approximately 30 days following discontinuation of all study treatment. For subjects that permanently discontinue all treatment prior to Week 25 Day 1, the Week 25 Day 1 visit should also be performed and may satisfy the requirement for the EOT visit if falling into the +30 days \pm 7 day window from all study drug discontinuation.

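### A missing last-dose date is imputed as the latest recorded date without limiting it to time on treatment, so an end-of-treatment or off-treatment Week 25 visit can stand in for the last dose

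*SAP*

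**What the plan says.** SAP 4.2.1 defines exposure: "Total duration of exposure to study drug will be defined as last dosing date minus first dosing date plus 1", expressed in weeks. For a missing last date it says "If the last study drug dosing date is missing, the latest date among the study drug end date, clinical visit date", followed by the laboratory sample date and the vital-signs date. The rule sets no cap at the study drug end date, at discontinuation or at 104 weeks, and it does not exclude visits made after treatment.

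SAP 3.6.1 makes this the general rule, not one for the exposure table alone: "For missing last dosing date of study drug, imputation rules are described in Section 4.2.1".

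The protocol schedules contact after treatment. Section 6.7 says "The EOT visit should be scheduled for 30 days following discontinuation of all study treatment". Footnote 19 of the schedule (Protocol Appendix 2, SAP Appendix 1) allows 7 days either side of day 30; in the SAP's words, the "7 day window from all study drug discontinuation". For subjects who stop all treatment before Week 25 without progression, Section 6.7 adds that "the Week 25 Day 1 visit should be performed on schedule per the Study Procedures Table". Protocol 3.5 agrees, with monitoring "up to Week 25 should a subject discontinue treatment prior to Week 25 for reasons other than disease progression". Both visits include hematology and chemistry, so they supply a visit date and a laboratory date.

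The SAP definition of a treatment-emergent adverse event (TEAE) in 7.1.5.1 ends "no later than 30 days after permanent discontinuation of study drug". The protocol definition in 8.6.2 instead counts 30 days from the last dose.

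**The concern.** Taking the maximum lets a later off-treatment contact override a recorded study drug end date. The rule resembles a data-cut convention for subjects still on drug, for whom the latest contact is a fair stand-in. That reason does not apply here: SAP 2.1 plans no interim analysis, and under SAP 2.2 the final analysis follows completion or discontinuation by every subject. The post-treatment visits will already be in the database.

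Two things are at stake. First, exposure duration: a subject who stopped early can be counted as having stayed on drug for months, in a trial whose secondary objective is safety and tolerability. Second, the safety windows tied to the last dose:

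- laboratory summaries, treatment-emergent laboratory abnormalities, liver tests and shift tables (SAP 7.2 to 7.2.4);
- the split of deaths at 30 days (SAP 7.1.6.1.1);
- TEAE status for events with incomplete onset dates (SAP 7.1.5.2);
- the end of the concomitant-medication period (SAP 7.4.2);
- the TEAE definition in Protocol 8.6.2.

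**Working it through.** The plan gives no figure to reproduce here. The check applies the SAP's own date arithmetic. True last-dose days are assumptions, shown over a range.

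**Inputs**
- Exposure in weeks = (last date − first date + 1) / 7, which is the study day of the last dose divided by 7 (SAP 4.2.1).
- EOT = last dose + 30 days, range 23 to 37 (Protocol 6.7; schedule footnote 19).
- Week 25 Day 1 = 24 × 7 + 1 = study day 169; with the 7-day visit window, days 162 to 176.
- Last-dose safety window = last dose + 30 days.
- Maximum oral treatment = 104 weeks = 728 days (Protocol 3.3).

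**EOT date used as the last dose**
- Excess exposure: 23/7 = 3.3, 30/7 = 4.3 and 37/7 = 5.3 weeks.
- The 30-day window then closes 23 + 30 = 53, 30 + 30 = 60 or 37 + 30 = 67 days after the true last dose.
- True last dose on day 28: 28/7 = 4.0 weeks becomes 58/7 = 8.3. The subject enters the category of at least 8 weeks.
- Completer, last dose on day 728: 104.0 weeks becomes 758/7 = 108.3, above the protocol maximum.

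**Off-treatment Week 25 visit (day 169) used as the last dose**

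| Assumed true last dose | True exposure (weeks) | Imputed (weeks) | Excess (weeks) | Window closes, days after true last dose |
|---|---|---|---|---|
| Day 28 | 4.0 | 24.1 | 20.1 | 141 + 30 = 171 |
| Day 84 | 12.0 | 24.1 | 12.1 | 85 + 30 = 115 |
| Day 140 | 20.0 | 24.1 | 4.1 | 29 + 30 = 59 |

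For the day-28 stop, the visit window of days 162 to 176 gives an excess of 19.1 to 21.1 weeks.

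**One oral drug stopped, the other continued.** Protocol 6.5 allows this. Suppose one drug stops on day 84 and its last date is missing. The Week 105 visit (day 104 × 7 + 1 = 729) gives 104.1 weeks and an EOT on day 758 gives 108.3, against a true 12.0. The candidate dates therefore have to be limited drug by drug.

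**Effect on a summary.** Per missing date in an arm of 30, mean exposure rises by (30/7)/30 = 0.14 weeks by the EOT route, or (141/7)/30 = 0.67 weeks by the Week 25 route after a day-28 stop. In a cumulative exposure category, one subject is 1/30 = 3.3% of Arm B and 1/6 = 16.7% of Arm A.

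**The case against.** The strongest reply is that the rule will seldom matter. Because EOT is scheduled from the stop date, a site that times it properly knows that date. Protocol 9.1.5 requires drug start and end dates in the source records, and SAP 2.2 places the final analysis after queries are resolved. Missing dates are likelier after death, loss to follow-up or withdrawal. Such subjects often have no later visit, and the latest contact is then a reasonable substitute. All of this stands as a limit on frequency. It does not rescue the rule, which still discards a recorded end date whenever a later visit exists.

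A reader might infer that every TEAE cut-off moves with the imputed date. The documents do not support that. SAP 7.1.5.1 runs from permanent discontinuation, and SAP 4.1 summarises discontinuation for each drug. Fully dated events move only if the discontinuation date is itself derived from the imputed last dose. Protocol 8.6.2 does count from the last dose, and SAP 7.7 declares no departure from the protocol's safety analyses, so the exposure of TEAEs to this rule is unclear rather than established. The supply of late events is also limited: Protocol 7.3 collects adverse events to 30 days after the last dose, although 6.2.10 speaks of recording them throughout the study.

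A reader might also suppose that every subject has an EOT visit. Death, loss to follow-up and withdrawal can prevent it (Protocol 3.4 and 3.6), and a suitably timed Week 25 visit may serve as EOT. Nor do vital signs contribute much: Protocol 6.2.4 puts only the screening values on the eCRF, and SAP 7.3 allows for unscheduled ones.

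Finally, the visible text plans no exposure-adjusted event rates, no testing and no comparison of arms. Inflated exposure therefore dilutes no event rate. Widened windows would over-count events, and the listings would show them.

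**Conclusion.** The point holds as a defect in a stated derivation, of minor importance. When a last-dose date is missing and a post-treatment visit was attended, the rule as written gives a date that is too late. Exposure is overstated by 3.3 to 5.3 weeks through EOT. Through an off-treatment Week 25 visit the excess depends on when the subject stopped: about 20 weeks for an assumed day-28 stop, about 4 for day 140. A missing date for one oral drug while the other continues could add more.

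The laboratory windows, the 30-day death split, the incomplete-onset rule and the concomitant-medication period move with it. The effect on fully dated TEAEs is conditional, as set out above.

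These sizes assume visits held as scheduled and the stated stop days. The documents do not say how many last-dose dates are missing; if none are, nothing changes. The Week 25 response rates are unaffected, because their window runs from the first dose (SAP 3.8.2.1).

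**What to change.** Replace the sentence in SAP 4.2.1 with a rule applied to each drug separately:

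1. If the recorded study drug end date (or the discontinuation date) for that drug is present, use it.
2. Otherwise use the latest visit or laboratory date on which the subject was still on that drug. Exclude EOT and any visit after that drug was discontinued, including an off-treatment Week 25 visit.

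Dispensing and return records can support the choice where available. They should not be the main source: visits are 12 weeks apart from Week 33, and SAP 4.2.2 already expects some unreturned bottles and missing return data.

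It would help to add to SAP 7.1.5.1 which recorded date defines permanent discontinuation, and to report how many last-dose dates were imputed for each drug.

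The main change costs one or two sentences and one derivation. It needs no new data and is harmless if no dates are missing.
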